[contact]
[contact]

SCHEMA

The Impact of CCR5 Inhibitor Treatment Intensification on CD4+ T-cell Recovery and Gene Expression Profiles in HIV-Infected Patients with Viral Suppression (Main Study)

Maraviroc Pharmacokinetics and Immunomodulatory Effects within the Central Nervous System (CSF Sub-Study)

Design:

CCTG 590 is a single-arm, open-label study to evaluate the impact of therapy intensification of Maraviroc (MVC) (a CCR5 inhibitor) to a stable suppressive HIV antiretroviral regimen on the rate of CD4+ T-cell recovery and gene expression profiles. Subjects on a stable first-line HIV regimen with continued viral suppression and sub-optimal CD4+ T-cell counts will be eligible for this study. Those who are found to be eligible will have MVC (dose-adjusted to background HIV regimen) added to their current HIV regimen for 24 weeks. After the 24 week intensification, the MVC will be discontinued, the original antiretroviral regimen will be continued and the subjects will be followed for an additional 12 weeks.

CCTG 590s is a central nervous system (CNS) sub-study that will evaluate MVC cerebral spinal fluid (CSF) pharmacokinetics and immunomodulatory effects within the CNS. The primary eligibility criteria will be enrollment into the MVC parent study, ability to give informed consent to lumbar puncture (LPs). Pre-treatment LPs will be performed, followed by a LP at week 4 of MVC treatment intensification (i.e., “steady state”). For subjects willing to undergo more than one LP, an additional LP will be performed at week 24 of MVC treatment intensification.

Duration:

Total study duration is 36 weeks: 24 weeks of MVC treatment intensification, followed by an additional 12 weeks of continued monitoring on baseline antiviral therapy without MVC.

Sample Size: 30 subjects (17 subjects for the CSF Sub-Study)

Study Population:

HIV-infected patients receiving an initial stable antiretroviral regimen with 12 months or more of viral suppression (defined by HIV RNA below detection limits) will be offered enrollment into this study. Eligible patients must have

documented dates of initiation of first HIV regimen and have been on continuous treatment for at least 15 months. In addition, available laboratory data must include at least 3 measurements of CD4 count and plasma HIV RNA loads obtained within the 12 months prior to screening.

Regimen:

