3.2 Study Design (CSF Sub-Study)

This is a sub-study of the MVC treatment-intensification protocol (i.e., a “piggyback” protocol). The primary eligibility criteria will be enrollment into the MVC parent study, ability to give informed consent to lumbar puncture (LPs), and the absence of medications or conditions that would contraindicate lumbar puncture (e.g., coagulopathy). Pre-treatment LPs will be performed, followed by a LP at week 4 of MVC treatment intensification (i.e., “steady state”). All LPs will be performed within one hour of a parent protocol-dictated blood draw, reducing the need for separate visits or additional phlebotomy. For subjects willing to undergo more than one LP, an additional LP will be performed at week 24 of MVC treatment intensification. The primary study outcomes will be measurement of MVC concentrations and reductions in markers of immune activation levels in CSF at week 4.

The study will aim to obtain 3 LPs in as many subjects as possible with the goal being at least two LPs separated by at least 4 weeks in up to 17 participants. After informed consent is obtained, subjects will undergo a brief screening to ensure the absence of contraindications to LP. If eligible subjects choose to enroll, subsequent visits will occur at major visits of the parent protocol (baseline, week 4 and 24). Based on prior experience we conservatively estimate that approximately 60% of subjects in the parent protocol will be willing to consent to lumbar puncture an average of 2.5 LPs per consenting subject. In total, we estimate that this CSF sub-study will yield approximately 43 LPs from individuals taking MVC. Post-dose timing of the lumbar punctures will be limited by the parent protocols but we will strive to vary the post-dose lumbar puncture interval in order to have approximately equal representation from two intervals.

- Interval 1: 2 - 6 hours post dose
- Interval 2: 6 - 12 hours post dose

If successful, this variation across the dosing interval will improve the accuracy of population pharmacokinetic modeling.

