3.6 Lumbar Puncture

Standard lumbar puncture-related adverse events will be monitored following all visits. Lumbar punctures will be performed under aseptic conditions at the clinical facilities of the HNRC by a neurologist, an internist, or by a trained registered nurse working under the supervision of the neurologist. Standard risks associated with HNRC medical procedures include 1) venipuncture: the risk of pain, bruising, and a very low risk infection; and 2) lumbar puncture: the risk of pain, bruising and a very low risk of infection as well as a risk of post-dural puncture cephalgia which can range from mild to severe.

Routine clinical lab assays (cell counts, glucose, total protein) will be performed on all CSF. HIV RNA will be measured with a modified version of the Biomerieux assay validated to quantify HIV as low as 2 copies/mL in CSF [51]. MVC concentrations will be measured in plasma and CSF. Remaining specimens will be aliquoted and then stored at -70C at the HIV Neurobehavioral Research Center (HNRC) Specimen Bank.

Local back pain will be minimized by injection of an anesthetic, 1% lidocaine into the subcutaneous tissue surrounding the needle puncture site. Oral analgesics and anti-inflammatory medications will be provided when necessary. Following LP, patients will be observed for 10-15 minutes. Over 3,000 LPs have been performed at the HNRC using non-cutting or "pencil point" spinal needles that reduce the risk of post-LP cephalgia. A site clinician will be available by pager 24 hours-per-day to respond to problems, should they occur. If post-LP headache occurs, initial conservative management will include recumbency, hydration, and oral analgesics. When headaches are prolonged, a blood patch, involving an epidural injection of a sample of the subject's own blood, may be performed by consulting anesthesiologists. This is extremely effective in aborting post-LP headache, but is only necessary in fewer than 1% of HNRC subjects. Palliative procedures will be performed at no cost to the participant.

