6.3.6 Clinical Assessments

Complete Physical Exam

A complete physical examination will be performed at entry. Documentation must include a complete review of systems and any HIV-related, toxicity-related, or AIDS-defining events.

Targeted Physical Exam

A targeted physical examination will be based on any signs or symptoms previously identified that the subject has experienced within 30 days of entry or since the last visit. This examination will be performed at entry, weeks 12, 24 and 36 and in instances of virologic failure or premature treatment discontinuation if they should occur. Documentation must include any HIV-related, toxicity-related, or AIDS-defining events.

Height and Weight

Height and weight should be measured at study entry.

Signs and Symptoms

All signs, symptoms, deaths, and toxicities must be documented in the subject's record. At entry, record all signs/symptoms experienced within 30 days of entry on the CRFs. For all other visits including the time of confirmation of virologic failure, record all Grade ≥ 2 signs and symptoms, HIV-related and AIDS-defining events and deaths on the CRFs that have occurred since the last visit. Any signs or symptoms that lead to a change in treatment, regardless of Grade, must be recorded on the CRF. The source document must include date of onset and date of resolution, but the CRF will only record prevalence of a given adverse event since the previous study visit.

Refer to the Division of AIDS Table for Grading Adult Adverse Experiences, which can be found on the CCTG website: www.cctg.ucsd.edu

Diagnoses

The following should be recorded on the CRFs: HIV-related diagnoses, HIV-related malignancies, non-HIV related malignancies, myocardial infarctions,

hepatic failures, AIDS-defining events and death. Any other diagnosis that is, in the opinion of the site investigator, associated with study medications, should be recorded on the adverse event CRF. The source document must include date of diagnosis and date of resolution.

Karnofsky Performance Status

A Karnofsky performance status must be completed within 30 days before study entry.

Vital Signs

Temperature, pulse, and blood pressure collected at all visits and kept as a part of the source document.

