5. Association between change in early immune subsets and phase 2 CD4 recovery will be assessed via Pearson's correlation analysis.

6. MVC plasma to CSF ratios at weeks 4 and 24 will be reported via descriptive statistics. Differences in MVC concentration ratios between subjects receiving a PI/r- vs. NNRTI-based background regimen will be compared via McNemar's test or paired t-tests as appropriate.

7. Descriptive statistics of CNS markers of immune activation will be reported via descriptive statistics. Differences in CNS markers of immune activation between baseline and weeks 4 and 24 will be compared cross-sectionally via McNemar's test or paired t-tests as appropriate.

8. Association between change in CNS markers of immune activation and MVC plasma to CSF ratios will be assessed via Pearson's correlation analysis.

9. Descriptive statistics of toxicity/intolerance during MVC treatment intensification will be reported via descriptive statistics. Differences in proportions of grades > 2 laboratory abnormalities and signs and symptoms will be compared via McNemar's test between time points.

10. Virologic failure during MVC treatment intensification will be reported via descriptive statistics.

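### Lumbar-puncture events are not separated in the maraviroc safety analysis: they can only raise the any-cause on-drug rate, by an unknown amount, and no LP safety table is planned

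*Combined protocol and SAP*

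**What the plan says.** **LP exposure.** The Schema plans 30 subjects, 17 of them in the CSF sub-study. Section 3.2 states the target as a ceiling: "goal being at least two LPs separated by at least 4 weeks in up to 17 participants". The laboratory schedule in section 6.1 places LPs at entry (day 0), week 4 and week 24. Section 3.2 makes the week-24 LP optional and calls the first one pre-treatment. Section 6.2.1 has the first MVC dose given at the entry visit, after the entry draw. Section 5.1.3 stops MVC at 24 weeks.

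**LP harms.** Section 3.6 says "Standard lumbar puncture-related adverse events will be monitored following all visits". The risks it names are pain, bruising, infection and "a risk of post-dural puncture cephalgia which can range from mild to severe".

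**Recording.** Under section 6.3.6, entry captures signs and symptoms from the preceding 30 days, and later visits capture those of Grade 2 or higher since the last visit, with no restriction by cause. Onset and resolution dates stay in the source document; "the CRF will only record prevalence of a given adverse event since the previous study visit".

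**Analysis.** Item 9 of section 9.4.3.1 reads "Descriptive statistics of toxicity/intolerance during MVC treatment intensification will be reported via descriptive statistics" and then compares proportions above grade 2 between time points by McNemar's test. It has no split by sub-study participation and no LP attribution. Neither section 9.2.2 nor section 9.4.3.1 lists an LP safety endpoint or table.

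**Threshold.** Objective 1.2.4 and item 9 use events above grade 2. Endpoint 3 of section 9.2.2 uses Grade 2 or higher.

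**The concern.** Tolerability of adding MVC is a stated secondary objective (1.2.4), and the trial is single-arm. No control group with the same LPs would reveal or cancel the contribution of the procedure.

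The procedure is scheduled, is done only for the sub-study, and is planned in up to 17/30 = 57% of subjects. Its first occurrence falls on the day MVC starts. Headache or back pain after the day-0 LP is reported at week 2 as an on-MVC event; after the week-4 LP it is reported at week 8. The entry look-back contains no scheduled LP. In an entry-versus-week-2 or entry-versus-week-8 McNemar comparison, LP events can therefore appear only on the MVC side.

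Because the CRF holds only interval prevalence, an analyst working from the CRF cannot see whether a symptom followed an LP. Clinical pattern may not settle it either: back pain after an LP overlaps with the musculoskeletal symptoms that the Safety and Tolerability section lists for MVC.

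Two things are at stake: whether the on-MVC event rate can be read as tolerability of MVC, and whether the sub-study produces a usable account of LP safety.

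**Working it through.** **1. The plan's own LP count.** Section 3.2 assumes "approximately 60% of subjects in the parent protocol will be willing to consent to lumbar puncture an average of 2.5 LPs per consenting subject" and concludes "we estimate that this CSF sub-study will yield approximately 43 LPs from individuals taking MVC".
- 17 × 2.5 = 42.5, which rounds to 43. Reproduced.
- Using the 60% directly: 0.60 × 30 = 18 subjects and 18 × 2.5 = 45 LPs, close to the stated figure.
- The 43 includes about 17 pre-treatment LPs. Those at weeks 4 and 24 number about 17 × 1.5 = 25.5.

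**2. Which LPs feed on-MVC windows.**

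| LP | Number | Events reported at | MVC status |
|---|---|---|---|
| Day 0 | 17 | Week 2 | on |
| Week 4 | 17 | Week 8 | on |
| Week 24 | 17 × 0.5 = 8.5 | Week 36 | stopped |

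Share feeding on-MVC windows: 34/42.5 = 80%.

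**3. Possible size.** The documents give no LP adverse-event rate, so the following inputs are assumptions:
- h = probability of a qualifying event per LP;
- p = probability that a subject has a qualifying on-MVC event for another reason, 10% to 40%;
- LP events are independent of each other and of background events;
- all 17 subjects have the first two LPs.

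Subjects with at least one on-MVC LP event = 17 × [1 − (1 − h)²].
Points added to the 30-subject rate = 100 × (17/30) × (1 − p) × [1 − (1 − h)²].

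| h | 1 − (1 − h)² | Expected subjects of 17 | Chance of at least one | Points added (p = 40% to 10%) |
|---|---|---|---|---|
| 1% | 0.020 | 0.34 | 0.29 | 0.7 to 1.0 |
| 5% | 0.098 | 1.66 | 0.83 | 3.3 to 5.0 |
| 10% | 0.190 | 3.23 | 0.97 | 6.5 to 9.7 |

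Worked case, h = 5% and p = 10%: 100 × 0.567 × 0.90 × 0.0975 = 5.0 points. For scale, one subject is 1/30 = 3.3 points.

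**4. The only documented anchor.** Section 3.6 says a blood patch is needed in fewer than 1% of the center's subjects. As a rough stand-in for LP events above grade 2: fewer than 17 × 0.01 = 0.17 subjects, and 0.17/30 is under 0.6 points. A blood patch is a treatment for prolonged headache, not a toxicity grade, so this is an indication and not a bound.

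**5. Dependence on the threshold.** Step 4 is the nearer guide for objective 1.2.4 and item 9 (above grade 2). The 5-10% rows in step 3 apply to endpoint 3 of section 9.2.2 (Grade 2 or higher).

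**The case against.** **Any-cause reporting is legitimate.** Objective 1.2.4 asks for an event rate, not a causal one, in a pilot. This stands, and it is why the any-cause rate should remain the main result. It does not remove the need to show how much of that rate may come from a scheduled procedure unrelated to MVC.

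**The effect may be negligible.** At the threshold that item 9 uses, the one documented figure points to under 0.6 points, and section 3.6 describes needles chosen to reduce headache. This stands for events above grade 2. It does not settle Grade 2 or higher, which section 9.2.2 specifies.

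**The McNemar comparison need not lean towards harm overall.** Item 9 does not say which time points are compared. The entry look-back is 30 days and the week-2 interval about 14, which works against seeing more events at week 2. This stands: the net direction is not established. What holds is narrower, namely that LP events can enter only the on-MVC side of such a comparison.

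**LP harm is not hidden.** A reader might infer from the missing table that LP harm goes unreported. The documents do not support that. LP events are monitored (3.6), Grade 2 or higher symptoms reach the CRF (6.3.6), clinical data enter the monthly toxicity reports (9.5), and serious events are reported (10.4). What is missing is a planned separate tabulation.

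**Attribution is a judgment.** Removing LP-attributed events from the main analysis could conceal real MVC toxicity. A flag on anything that starts after an LP, with no time limit, would catch nearly every on-study event in a subject with a day-0 LP. Both points stand and limit the fix.

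**Conclusion.** The point holds in limited form. Item 9 mixes LP events with other on-MVC events, about 80% of planned LPs feed on-MVC windows, and no LP safety table is planned. Including LP events can only raise the any-cause on-MVC rate.

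The size cannot be fixed from the documents: under about 0.6 points for events above grade 2 on the blood-patch proxy, and about 3 to 10 points for Grade 2 or higher if 5-10% of LPs cause such an event against a background of 10-40%. The event and background rates are assumptions. If fewer than 17 subjects join, the effect shrinks in proportion.

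Three stronger readings should be avoided:
- Seventeen is the planned ceiling of subjects having an LP, not a count of subjects with complications.
- Not every LP bears on the on-MVC rate: MVC stops at the week-24 visit, so events after that LP arise off drug.
- The 4.9% in the Safety and Tolerability section is a rate of discontinuation due to adverse events, so it is no benchmark for these any-event figures.

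This is a cheap improvement to the interpretability of a secondary objective. It does not show that the tolerability rate will be materially wrong.

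**What to change.** In section 9.4.3.1, item 9:

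1. Keep the any-cause on-MVC rate as the main result.
2. Report it also for CSF sub-study participants and non-participants separately.
3. Add a CRF flag for LP-related events, based on the onset date already held in the source document and a post-LP time window fixed before analysis. Show the rate and the McNemar comparisons with and without flagged events, as a sensitivity analysis only. Name the time points to be compared.
4. Add a sub-study safety table of LP-related events per LP performed, by day 0, week 4 and week 24. This also covers events after the week-24 LP, which a summary restricted to the intensification period would miss.
5. Reconcile the grade threshold across objective 1.2.4, endpoint 3 of section 9.2.2 and item 9.

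The cost is SAP wording, one CRF field and one or two tables, with no extra visits or procedures. The drawback is precision: 30 − 17 leaves about 13 subjects without an LP, so that rate will be imprecise and the split should be read descriptively.

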1.2 Secondary Objectives

- 1.2.1 To compare the rates of phase 2 CD4+ T-cell recovery prior to and during 24 weeks of MVC therapy intensification.
- 1.2.2 To evaluate the impact of MVC therapy intensification on persistent immune activation and maturation phenotype (as measured by flow cytometry) during viral suppression.
- 1.2.3 To characterize differences in the gene expression profiles associated with MVC therapy intensification in individuals receiving a PI/r- vs. NNRTI-based regimen.
- 1.2.4 To evaluate the safety and tolerability of adding MVC to a stable antiretroviral regimen as assessed by the rate of > grade 2 adverse clinical or laboratory events.
- 1.2.5 To characterize cerebral spinal fluid concentrations of MVC compared to plasma concentrations.
- 1.2.6 To evaluate the impact of MVC therapy intensification on persistent immune activation (as measured by soluble and cellular markers) in the central nervous system.

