9.2.2 Secondary

1. CD4+ T-cell absolute count and percentage at baseline, weeks 4 and 24.
2. The proportion of CD4+/CD8+ T-cell immune activation, maturation, regulatory and apoptosis markers at baseline and weeks 4 and 24.
3. Grades ≥ 2 laboratory abnormalities and signs and symptoms.
4. Paired plasma to CSF ratios of MVC concentration at week 4.
5. Soluble immune activation markers in CSF at baseline and week 4.
6. HIV RNA loads in CSF at baseline and week 4.

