9.3 Sample Size and Accrual

Sample size calculations are based on within-patient comparisons of gene expression profiles from baseline to week 24. The calculations required to make such comparisons will depend on several experimental parameters including biological variability of the samples within each class, the expected fold change to be detected, technical sensitivity of the microarray technology, and acceptable error rates of the results. As researchers in this field have shown [52], one way to ensure acceptable error rates is to control the false discovery rate (FDR), which is

equivalent to setting a minimum specificity. The FDR is the expected fraction of significant genes, which in practice, do not differ in reality. This differs from the false positive rate (FPR), which is the proportion of non-differentially expressed genes that, just by chance, appear to differ.

Determining the biological variability of the system is a difficult task, especially when there is no pre-existing data available. The ranges of conditions that can contribute to biological variability include environmental conditions, cell types, and genotypic variation [53]. Based on an extensive literature review, Zien et al. [53] conclude that a value of 0.4 provides a conservative estimate of the biological standard deviation (variability between and within classes of biological samples). We will consider biological standard deviation values of 0.4 for our power calculations. Further, we will consider a technical variation of 0.3 and 0.4.

As a conservative approach, we base the sample size calculations on the Wilcoxon Rank Sum test. This is a non-parametric procedure, in which no distributional assumptions are placed on the data. Using the on-line power calculator developed by Zien et al. [53] which computes sample sizes for microarray experiments, Table 1 provides the approximate statistical power for various biological variation, technical variations and signal-to-noise ratios. Here, we consider a Type 1 error of 0.01 and a fold change of 2. We assumed 500 hits from the 38,000 genes. Notice that these power calculations are based on the number of samples allocated to the training set (either 20 or 25 per group). The sample size calculations indicate fair power (60-80%) to find a difference in gene expression before and after maraviroc treatment.

Baseline (N)	Week 24 (N)	Biological Variation	Technical Variation	Signal-to-noise	Power
20	20	0.4	0.3	3	77%
20	20	0.4	0.4	3	68%

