9.4.3.1. Analysis of Secondary Objectives

Secondary analyses will include descriptive statistics and tests of significance between pre- and post-MVC intensification. All significance tests will be two-sided and no adjustment for multiple comparisons will be made. If necessary due to assumption failures, appropriate non-parametric statistical tests will be applied.

1. Differences in the change in CD4+ T-cell absolute count and percentage from baseline to week 4 and baseline to week 24 will be compared descriptively via separate paired Student t-tests. Repeated CD4+ T-cell absolute count measured at different time points (3 historic time-points, baseline, week 4, and week 24) will be treated as the outcome variable in a linear mixed-effects model. The primary fixed effects will include time, period (MVC vs. pre-MVC), and interaction between time and period; random effects will include both intercept and slope allowing each subject to have individual starting CD4+ T-cell counts and rate of change. Baseline covariate adjustment will be included if necessary. A significant interaction term between time and period with positive coefficient will indicate if the rate of CD4 recovery is greater during MVC compared to pre-MVC.

2. Differences in the rate of CD4+ T-cell recovery (absolute count and percentage) during MVC intensification in subjects receiving a PI/r- vs. NNRTI-based regimen will be compared via the linear mixed effects model. The fixed effects will include time, regimen (PI/r vs NNRTI), and regimen-by-time interaction; random effects will include both intercept and slope. The regimen-by-time interaction term in the model will indicate the difference in CD4+ T cell recovery rates between the two regimen groups. Baseline covariate adjustment will be included if necessary.

3. Differences in gene expression profiles between subjects receiving a PI/r vs. NNRTI-based regimen at baseline and weeks 4 and 24 will be examined by comparing the gene lists generated in the primary analysis by regimen type. If necessary, statistical modeling will include a dichotomous variable to indicate regimen type.

4. Differences in the proportion of CD4+/CD8+ T-cell immune activation, maturation, regulatory and apoptosis markers between baseline and weeks 4 and 24 will be compared cross-sectionally via McNemar's test or paired t-tests as appropriate.

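### The safety objective asks for a rate of adverse events on MVC, but the only planned inference is a between-time-point McNemar test that neither estimates nor bounds that rate

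*Combined protocol and SAP*

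**What the plan says.** Objective 1.2.4 (Section 1.2) sets out to evaluate safety and tolerability "as assessed by the rate of > grade 2 adverse clinical or laboratory events". The matching entry in the endpoint list, Section 9.2.2, uses a different threshold: "Grades ≥ 2 laboratory abnormalities and signs and symptoms".

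Item 9 of Section 9.4.3.1 has two sentences. The first is "Descriptive statistics of toxicity/intolerance during MVC treatment intensification will be reported via descriptive statistics". The second is "Differences in proportions of grades > 2 laboratory abnormalities and signs and symptoms will be compared via McNemar's test between time points". Item 10 handles virologic failure descriptively as well: "Virologic failure during MVC treatment intensification will be reported via descriptive statistics".

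The preamble to the secondary analyses says "All significance tests will be two-sided and no adjustment for multiple comparisons will be made". It gives no significance level. The only one in the document belongs to the gene-expression power calculation in Section 9.3: "Here, we consider a Type 1 error of 0.01 and a fold change of 2". Section 9.1 says the study is powered for gene expression.

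No confidence interval, upper bound, unacceptable rate or power figure for safety appears anywhere. The version of McNemar's test (exact, corrected or uncorrected) and the time points to be paired are not named.

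**The concern.** The objective is an estimation question: in what proportion of subjects does adding MVC come with an event above the threshold? A McNemar test answers another question, namely whether the marginal proportions at two time points differ. It uses only subjects whose status changed and returns a p-value, with no rate and no range for the rate.

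In a single-arm study of 30 subjects that p-value would be the only inferential statement on tolerability. If it comes out non-significant, as is likely even with a sizeable number of new events, the report holds nothing that shows how high the true rate could still be. The subjects are already virologically suppressed on their background regimen, so tolerability weighs heavily in any benefit-risk statement.

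**Working it through.** **1. What the test compares**

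- *Recall windows.* Section 6.3.6 records signs and symptoms over the 30 days before entry, and afterwards over the time since the previous visit. By the visit schedule the week 2 record covers 2 weeks and the week 24 record covers 24 − 12 = 12 weeks. An entry-versus-week-24 pair therefore sets about 4 weeks against about 12.
- *Missing pairs.* Section 6.2.3 replaces subjects who stop MVC or antiretroviral therapy before week 4 and plans no follow-up evaluations for them. Sections 7.1.2, 7.2.3 and 7.2.4 remove subjects from the study after resolution of a symptomatic MVC-related Grade 3 event, a Grade 4 event requiring permanent discontinuation, or a Grade 3 or 4 rash not judged unrelated to MVC. Such subjects may have no later scheduled record to pair. Section 6.2.4 instead keeps on study those who stop after week 4. These passages conflict and must be reconciled.
- *Laboratory baseline.* The Schedule of Events shows no chemistry or liver-function draw at entry, so those pairs would have to start from screening. Item 9 does not say so.

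**2. Sensitivity of one comparison**

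The plan states no figure to reproduce. Inputs:

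- n = 30 pairs: the planned sample size, all pairs complete.
- Two-sided test: from the plan. Alpha 0.05: assumed.
- Probability of a new event p = 0.10, with 0.15 and 0.20 as alternatives: assumed.
- No event present at entry, so c = 0 (c counts subjects whose event resolves, b those with a new event): assumed, and favourable to the test.

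Smallest b that is significant when c = 0:

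- Exact: p-value = 2 × 0.5^b. For b = 5 it is 0.0625; for b = 6 it is 0.031. So 6 are needed.
- Continuity-corrected: (b − 1)²/b. For b = 5 it is 3.20; for b = 6 it is 4.17, above 3.84. So 6 are needed.
- Uncorrected: b²/b = b, so 4 are needed.

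The miss rate is P(X < threshold) with X ~ Binomial(30, p). At p = 0.10, P(X ≤ 3) = 0.6474. Adding P(4) = 0.1771 and P(5) = 0.1023 gives P(X ≤ 5) = 0.9268.

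| New-event rate | Missed, uncorrected | Missed, exact |
|---|---|---|
| 10% | 65% | 93% |
| 15% | 32% | 71% |
| 20% | 12% | 43% |

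Power of 80% needs a new-event rate of about 18% (uncorrected) to 25% (exact).

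Varying one input at a time at 10% new events:

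| Change | Missed |
|---|---|
| 2% of subjects have an entry event that resolves | 79–95% |
| 5% of subjects have an entry event that resolves | 91–98% |
| 27 complete pairs | 72–95% |
| 24 complete pairs | 79–97% |
| Alpha 0.01 | 97–99.8% |

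**3. What an interval would show**

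The Clopper-Pearson two-sided 95% upper limit for x of 30 is the 0.975 quantile of Beta(x + 1, 30 − x). For x = 0 it is 1 − 0.025^(1/30) = 0.116.

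| New cases | 95% interval | Exact McNemar p (c = 0) |
|---|---|---|
| 0/30 | 0 to 11.6% | 1.0 |
| 3/30 | 2.1% to 26.5% | 0.25 |
| 5/30 | 5.6% to 34.7% | 0.0625 |

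**The case against.** The strongest reply has five parts.

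- *The plan never says that non-significant means safe.* This is correct. A reader might infer that reading from the absence of any other inference, but no passage states it, so it is not charged here.
- *Item 9 already promises descriptive statistics over the treatment period, and a reported x/30 lets anyone compute an interval.* This partly stands: a rate may well be reported, so it would be too strong to say the objective goes unanswered. But item 9 does not specify a per-subject proportion at any time on MVC, its denominator, or an interval.
- *The low power comes from n = 30 in a pilot, not from McNemar.* This stands. An interval adds no information about harm; it shows the uncertainty that the p-value hides. With no unacceptable rate in the protocol, the upper limit informs a statement and decides nothing. That a study is a pilot favours estimation over testing.
- *McNemar is the only baseline-referenced comparison.* This stands and shapes the fix. Criterion 4.1.9 admits AST, ALT and alkaline phosphatase up to 5 × ULN and waives the bilirubin limit for atazanavir recipients. A bare count of on-MVC events would include abnormalities present before MVC.
- *Monitoring protects subjects.* Section 9.5 provides monthly toxicity reports and independent review after more than five virologic failures or toxicity discontinuations. That is a review trigger and does not bound the rate. At a combined rate of 10% among 30 subjects it fires with probability P(X ≥ 6) = 7.3%.

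A reader might also take the 10–20% scenarios as harms that MVC is expected to cause. The documents do not support that. The controlled data in the safety background show small differences (AST 4.5% vs 2.9%, ALT 2.4% vs 3.4%, bilirubin 5.7% vs 5.3%), and a single-arm study cannot attribute cause.

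**Conclusion.** The point holds as a mismatch between objective and analysis. The only planned safety inference does not estimate the rate named in the objective, compares unequal recall windows for signs and symptoms, can lose subjects who stop or are removed for toxicity, and comes with no interval. The 65–93% miss rate applies to a single comparison under the assumptions listed in the working. The 65% end belongs to the uncorrected chi-square, which is unreliable with so few discordant pairs. Several unadjusted comparisons would somewhat raise the chance of at least one significant result; missing pairs, resolving entry events or a stricter alpha would raise the miss rate.

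It would go too far to say that the test cannot detect any relevant harm: at 20% new events the uncorrected version has about 88% power. What follows is narrower: a non-significant result cannot carry a tolerability statement. The change is worth making before analysis, and it concerns reporting rather than study conduct.

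**What to change.** In item 9 of Section 9.4.3.1:

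- Make the main safety summary the number and proportion of subjects with at least one treatment-emergent event of the qualifying grade at any time on MVC, with an exact (Clopper-Pearson) 95% confidence interval, separately for clinical and laboratory events.
- Define the denominator as all subjects who took at least one dose, including those replaced before week 4. It may then exceed 30.
- Define treatment-emergent as new, or worsened in grade, relative to the entry value, or the screening value where nothing is drawn at entry.
- Keep McNemar only as a descriptive baseline-referenced comparison, naming the version and the time points. State that a non-significant result is not evidence of safety.
- Reconcile the grade threshold (> 2 in objective 1.2.4 and item 9, ≥ 2 in Section 9.2.2), and reconcile Section 6.2.4 with the removal rules in Section 7.

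The cost is SAP wording and a few lines of code, using records the protocol already collects. One limit should be stated: because Section 6.2.3 plans no follow-up for subjects who stop before week 4, they contribute only what was recorded up to stopping, plus any serious events reported under Section 6.4. The downside is a less favourable safety statement, since even 0/30 leaves rates up to 11.6% open.
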